4.0 STUDY PLAN

4.1 Schema

This study will test the feasibility of a two-group randomized controlled pilot trial using pre-post mixed-method design. This pilot intervention study of 70 patients with newly diagnosed localized prostate cancer and their partners (70 couples) will examine the feasibility of ESCPs and the initial benefit of ESCPs. We anticipate that patient study participation will last at least 4 months.

Use of regular SCPs is routine, usual care at the GU clinics at UNC LCCC and Duke Cancer hospital. When a patient returns to the clinic about 2 weeks after initial treatment, his provider will complete and print a standardized SCP adapted from the American Society of Clinical Oncology (ASCO) template (see Appendix for example), review it with the patient/family in a private room behind a closed door, and provide him with a copy. The SCP will also be sent to his primary care provider via electronic health record (EHR) or fax. The SCP section about possible late- and long-term treatment effects provides a generic summary of the side effects of all types of treatment, options for managing the side effects, and recommendations for diet, physical activities, smoking cessation, and stress. All of this information is brief and presented in bullet points. One of the GU clinics is encountering a major nursing staff turnover, causing omission of SCP implementation to most patients at the clinic. While the clinic is hiring new nursing staff, an oncology nurse practitioner student who is also a staff nurse at the cancer hospital will work closely with the nurse practitioners, physician assistant, and nurse navigators to help generate and deliver the survivorship care plans with the embedded study website to eligible patients.

Participant involvement and time commitment (estimates based on our previous research)

Participant involvement	Time commitment (Minutes)
Recruitment and consent for study	
Recruitment information (introduction of study, consent information)	3-5
Recruitment, eligibility, and informed consent in-person or via telephone: patients	10
Recruitment, eligibility, and informed consent in-person or via telephone: partners of eligible patients	10
Baseline survey in person or via telephone (T1)	
For patients who are eligible	30-45
For partners who are eligible	30-45
Complete and return the receipts for the gift cards	2
The SCP review and instruction of the study website use	5-10
Moderated online Forum/meeting upon request	Variable

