4.2 Duration of Study

Participants in the ESCP group (regular SCP+PERC web link) will be able to select the intervention modules depending on the number of symptoms the patients have, and thus, the duration of participation will range between 4 weeks to 12 weeks. All participants will complete a follow-up survey at around 4 months post-baseline. See the table below for participant time commitment.

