5.1 Time and Events Table

	Baseline (T1)	Intervention	4 months post-baseline (T2)	Post-exit interview	
Screening	X	SCP vs ESCP			
Informed Consent	X				
Randomization	X				
Quality of Life	X			X	
Appraisal of prostate cancer symptoms	X			X	
Self-efficacy in symptom management	X			X	
Social support	X			X	
Health behaviors	X			X	
General symptoms	X			X	
Prostate cancer symptoms	X			X	
Comorbidities (Charlson index)	X			X	
Demographic characteristics	X				
Program satisfaction				X	
Perceived ease of use				X	
Participants' experiences of using the programs					X
Medical Records Abstraction	Continuously throughout study				

SUMMARY OF MEASURES AT BASELINE (T1) AND 4 MONTHS POST-BASELINE (T2)						
VARIABLES AND MEASUREMENT	DATA SOURCE A	GROUP	T1	T2	CRONBACH ALPHA	PERC PROGRAM ^C
Aim 1: Feasibility of ESCP						
Screening, Enrollment, and retention rates: research activity logs; field notes	AD	Both	X	X	na	na
Self-reported program use	PT, SP	Both		X	na	na
Web activity of using PERC: visit PERC or not, Number of logins, time spent on PERC, Use of modules and links	Tracking system	ESCP	X	X	na	
PERC session reviewed: # of reviewed sessions; % of reviewed sessions consistent with reported PCa symptoms	AD	ESCP		X	na	Built in tracking system in PERC
Program satisfaction and perceived ease of use: Usability Scale ^{82,83}	PT, SP	Both		X	na	na
Participants' experiences of using the programs: Exit Interview	PT, SP, AD	Both		X	na	na
Aim 2: Magnitude of benefits of ESCP for Survivor-Partner Couples (Compared with SCP only couples)						
MAIN OUTCOMES: Quality of Life (Overall, physical, emotional, and social well-being): Functional Assessment of Chronic Illness Therapy General Scale (27-item FACT-G) ^{82,101}	PT, SP	Both	X	X	0.90 ^{26,82}	All
Number of visits to post-treatment care services: Medical records	HER, PT	Both		X	na	All
Appraisal of PCa symptoms: 4-item Bother Questionnaire ^{25,26}	SP	Both	X	X	0.74-0.9 ^{25,26}	All
Self-efficacy in symptom management: 9-item Cancer Self-Efficacy Scale ¹⁰²	PT, SP	Both	X	X	0.91-0.96 ²⁵	All
Social Support: Adapted supportive interaction scale ¹⁰³	PT, SP	Both	X	X	0.74-0.86 ¹⁰³	PA; CR
Health behaviors: Physical Activity and Nutrition in Health Promoting Lifestyle Profile II. ^{104-107*}	PT, SP	Both	X	X	0.75-0.92 ^{106,107}	HB; CR
ANTECEDENTS (CONTROL VARIABLES): PARTICIPANT CHARACTERISTICS						
Demographic Characteristics: age, race/ethnicity, income, education, and etc.	PT, SP	Both	X		na	na

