behaviors from T1 to T2 among patients and partners, we use a two-sample t test with an effect size measured by Cohen's d .¹¹⁴ A sample size of 23 couples per group yields 80% power to detect a moderate/large effect size of 0.74 at the one-sided 0.05 significance level. Power calculations were performed using the **pwr** package in R (version 3.2.3).

We estimate power in testing our hypothesis that ESCP and SCP patients differ in the number of visits to post-treatment care services at T2 in the context of a Poisson regression model, using a right-tailed F test. Assuming that patients in the SCP only group average 6 post-treatment care visits at T2, a sample size of 23 patients per group yields 85% power to detect an increase or decrease of 33.3% in the average number of post-treatment care visits for patients in the ESCP group (i.e., 4 or 8 post-treatment care visits at T2) at the 0.05 significance level. Power calculations were performed using SAS Version 9.4.¹¹⁸

Due to the relative newness of SCPs and the complete novelty of ESCP for prostate cancer patients, we had no prior or historical information with regards to the difference between the SCP only and ESCP groups for these main outcomes. Therefore, we computed the effect sizes used for our power calculations based on the available sample size. We recognize that these effect sizes may not be reasonable guesses of the true effect sizes as a result, but due to budgetary concerns and time constraints, we thought it best to still proceed with our calculations.

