We will fit a Poisson regression model, using a logarithm link function, to the number of patient visits to post-treatment care services at T2. In fitting this model, we will include group membership as a predictor, while controlling for the following effects: PCa treatment type (since this was our stratification variable when we randomly assigned patients to a specific group), age, income, and the Charlson Comorbidity Index, EPIC score, and the General Symptom Scale score at T2. Based on this model, we will estimate the ratio of the model-predicted number of visits to post-treatment care services at T2 for the ESCP group to that of the SCP only group to address the hypothesis that ESCP and SCP patients differ in the number of visits to post-treatment care services at T2.

To assess the effect of group on QOL, self-efficacy in symptom management, social support, and health behaviors while accounting for the fact that couples have correlated measurements, we will fit a series of linear mixed models across both patients and partners. Specifically, we will fit a linear mixed model to the change score for each measure of the outcomes of QOL, self-efficacy in symptom management, social support, and health behaviors. In doing so, we will include the following as fixed effects: group membership (ESCP vs. SCP), couple member (patient vs. partner), type of prostate cancer treatment (our stratification variable), the outcome's measure at T1, age, income, the Charlson Comorbidity Index score, and the differences in the Charlson Comorbidity Index, EPIC scores, and General Symptom Scale scores between T1 and T2. To account for the correlation among each patient and partner in a particular couple, we will also include couple membership as a random effect. Since appraisal of prostate cancer symptoms is only measured in partners and number of post-treatment care visits at T2 is only measured in patients, we cannot conduct these exploratory analyses for these two outcomes.

Since this is an exploratory proof-of-concept study, rather than a confirmatory study, we will not adjust for multiplicity when analyzing any of the previously mentioned outcomes. We expect the findings from

these analyses to be confirmed in future RCTs and that they may be used for generating hypotheses and designing new studies.

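### The Poisson model for post-treatment visits compares raw counts with no exposure term, and the plan never secures an equal counting period for each patient

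*Combined protocol and SAP*

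**What the plan says.** Section 7.3 gives the model: "We will fit a Poisson regression model, using a logarithm link function, to the number of patient visits to post-treatment care services at T2". The predictors are group, treatment type (the stratification factor) and "age, income, and the Charlson Comorbidity Index, EPIC score, and the General Symptom Scale score at T2". No offset, rate or person-time appears there or elsewhere. The result is reported as a ratio of predicted visit numbers. The end of section 7.3 uses the mean count per group to size the future trial.

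On timing, section 4.2 says "All participants will complete a follow-up survey at around 4 months post-baseline", and section 5.0 also describes T2 as approximate. Sections 4.3, 5.1 and 7.1 give a plain 4 months. No section sets a visit window.

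On the counting period, the section 5.1 table lists medical records and the patient as sources of the visit count, and shows records abstraction as "Continuously throughout study". No start or end date for counting is given. Section 3.1 admits patients up to 4 weeks after treatment, so it matters whether visits count from treatment, baseline or randomisation. Section 4.3 also mentions collecting visit numbers alongside the exit interviews, which follow T2.

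The planning figures in section 7.2 are "Assuming that patients in the SCP only group average 6 post-treatment care visits at T2" and "4 or 8 post-treatment care visits at T2" in the ESCP group.

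**The concern.** A ratio of raw counts equals a ratio of visit rates only if the arms have the same average observation time. If observation varies between patients but not between arms, the ratio stays unbiased. The counts then vary more than the Poisson model allows, and its standard errors are too small. If average observation differs between arms, the ratio itself is biased. The plan has no device against either: no T2 window, no cut-off for counting and no exposure term.

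Visit numbers are listed among the main outcomes for the second aim in section 5.1, and their group means are an input to the next trial's sample size. An artefact here would be passed on.

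**Working it through.** **Reproducing the plan's figure.** Inputs from section 7.2 are 23 patients per group, a control mean of 6, an ESCP mean of 4 or 8, alpha 0.05 and a right-tailed F test (two-sided for the log ratio). Equal exposure is implicit.

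- Noncentrality = ln(m1/m0)² / (1/(n·m0) + 1/(n·m1)).
- 6 vs 4: 0.1644 / (1/138 + 1/92) = 0.1644 / 0.01812 = 9.07. Power is 0.838 with F(1,44) and 0.854 with the normal reference, so the stated 85% reproduces.
- 6 vs 8: 0.0828 / (1/138 + 1/184) = 0.0828 / 0.01268 = 6.53. Power is 0.705 to 0.724, so the 85% does not reproduce for an increase. That is a separate matter from this point.

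**Timing varies equally in both arms.** The documents give no distribution of T2 dates. Assume T2 uniform over 3 to 5 months and a constant 6/4 = 1.5 visits per month.

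- Variance of exposure = 2²/12 = 0.333 (SD 0.58 month).
- Added count variance = 1.5² × 0.333 = 0.75. Relative to the Poisson variance of 6, this is 12.5%.
- √1.125 = 1.061, so model standard errors are about 6% too small.
- The nominal 1.96 becomes 1.96/1.061 = 1.85, a two-sided error of about 0.065. A simulation of this case gave 0.063 and a ratio of 1.00.

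**Timing differs by arm.** Assume ESCP calls come two weeks (0.46 month) later on average. The null ratio becomes 4.46/4 = 1.115, a bias of about 12%.

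**Simulation.** Unadjusted comparison, 23 per arm, 6 visits per 4 months, true ratio 1, constant visit rate, 40,000 runs, t reference with 44 df. All exposure patterns are assumptions. With the offset, the ratio is 1.00 in every row.

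| Assumed exposure | Ratio, no offset | Type I error, no offset | Type I error, offset |
|---|---|---|---|
| 4 months for all | 1.00 | 0.044 | 0.043 |
| T2 uniform 3.5–4.5 months, both arms | 1.00 | 0.047 | 0.044 |
| T2 uniform 3–6 months, both arms | 1.00 | 0.070 | 0.043 |
| ESCP T2 two weeks later | 1.12 | 0.138 | 0.044 |
| 8% leave early in both arms, partial counts kept | 1.00 | 0.062 | 0.046 |
| 8% SCP and 20% ESCP leave early, partial counts kept | 0.94 | 0.103 | 0.043 |

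**Effect on sizing the next trial.** Patients per arm for 85% power, two-sided 0.05, is (1.960 + 1.036)² × (1/m0 + 1/m1) / ln(m1/m0)².

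- True means 6 vs 4: 8.98 × 0.4167 / 0.1644 = 22.8, so 23 per arm.
- ESCP observed two weeks longer, apparent mean 4.46: 8.98 × 0.3909 / 0.0880 = 39.9, so 40 per arm.
- ESCP observed two weeks shorter, apparent mean 3.54: 8.98 × 0.4492 / 0.2784 = 14.5, so 15 per arm.

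**The case against.** The strongest reply is that T2 is nominally 4 months for everyone, both arms share one telephone schedule, and randomisation balances ordinary variation in call dates. For variation of about two weeks either way, this stands: there is no bias and the type I error is 0.047. Nor does any passage indicate that ESCP calls would be later. Section 5.0 does justify the T2 date by completion of PERC, but PERC is due to end after 12 weeks (section 4.3) or at most 14 (section 4.1), before 4 months. The two-week difference is therefore a hypothetical that the plan fails to exclude, not one it predicts.

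Three stronger readings are tempting and should not be drawn:

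- A reader might take "We anticipate that patient study participation will last at least 4 months" (section 4.1) to mean that T2 itself can fall at any time after 4 months. That sentence describes length of participation, and exit interviews follow T2. Likewise, "Continuously throughout study" says when records are abstracted, not what period is counted.
- A reader might infer that the short counts of couples who leave early (section 4.5) enter the model as if they covered 4 months. The documents do not show this. The model needs T2 Charlson, EPIC and General Symptom scores, section 7.2 bases power on complete data, and no imputation is described. A patient without a T2 survey would drop out of the fit, despite the intention-to-treat statement in section 7.3. The last two table rows apply only if partial counts were kept.
- A reader might think an offset alone cures this. It does not restore patients whose T2 covariates are missing, and it assumes a roughly constant visit rate. Suppose 4 of 6 visits fall in the first 2 months, and 8% of SCP and 34% of ESCP patients leave at 2 months. Mean counts are 0.92×6 + 0.08×4 = 5.84 and 0.66×6 + 0.34×4 = 5.32, a null ratio of 0.91 without the offset. Relative exposures are 0.96 and 0.83, so with the offset the ratio is (5.32/0.83)/(5.84/0.96) = 1.05. That is better, but not unbiased.

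**Conclusion.** The point holds in limited form. The model has no exposure term, and the plan secures equal exposure neither by a T2 window nor by a defined counting period. With timing variation equal in both arms, the ratio is unbiased and the cost is modest: standard errors about 6% too small under the assumed 3-to-5-month spread, and next to nothing for two weeks either way. Bias arises only if timing or follow-up differs by arm. An assumed two-week difference gives about 12%, roughly a third of the 33.3% difference used for planning. All these magnitudes rest on assumed exposure patterns and a constant visit rate. This is a secondary outcome in an exploratory pilot, so the point is minor. It is worth acting on because the group means feed the next trial's sample size and the remedy is cheap.

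**What to change.** In sections 5.1 and 7.3:

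1. Define the outcome as visits from randomisation over the same fixed 4-month window for every patient, taken from medical records with visit dates, whatever the date of the T2 call. This should be the main approach.
2. Where the window is incomplete, keep the patient and add log(days observed) as an offset. Where it is complete for everyone, the offset changes nothing: simulated power for 6 vs 4 is about 0.84 to 0.85 either way.
3. To keep patients with shorter observation in the intention-to-treat analysis, replace the T2 Charlson, EPIC and General Symptom covariates with their T1 values, which section 5.1 already collects, or state how T2 values are imputed.

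The cost is a few sentences, one model term and some abstraction work. Sections 4.3 and 4.4 onward speak only of numbers of visits or do not address dates, so recording of visit dates cannot be assumed. Dates would have to be abstracted, and patient-reported visits may need dates added. The offset's constant-rate assumption should be stated, which is why it is confined to incomplete windows.

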7.4 Data Management/Audit

Per our consultation with the DSMB at UNC School of Medicine, although this is a pilot feasibility of a randomized clinical trial, a DSMB is not needed because this study is of such low risk. With one of the main outcomes as the change in QOL between the ESCP and SCP groups, there would not be anything significant to provide to the DSMB that might signal a reason for the DSMB to stop a study. However, we will implement a data and safety-monitoring plan to ensure the safety of participants and the validity and integrity of the data. The data monitoring plans are as follows.

A. The PI will convene weekly meetings with the research staff to review project progress, subject accrual, follow-up, and any anticipated and unanticipated problems. The PI will be responsible for monitoring study processes and ensuring that Adverse Events and Unanticipated Problems are reported to all relevant regulatory bodies.

B. The study consent obtained at the in-person interview at the clinic will be saved in a locked cabinet in a locked office. The consent obtained via telephone will be recorded and saved in a separate password protected and encrypted share drive at the UNC-Chapel Hill School of Nursing. The study consent will also clearly state that de-identified research data may be shared with other researchers after study completion. The research staff will explain the purpose of data sharing and the associated procedures to potential participants, as well as answer their questions related to this study.

C. Study data will be collected and stored using REDCap online database, managed by the TraCS Clinical Research Data Management Service. NC TraCS is a key initiative of the Biomedical Informatics core of the UNC-Chapel Hill CTSA. The purpose is to provide a system, and associated support resources, to enable efficient and high quality collection and management of research data that is standards-based in design, development and implementation. Standard features of electronic clinical research data management systems are available in the web-based systems provided with the service. These include interactive data entry with real-time field validation, lab data imports, audit logs to record database modifications, database integrity checks, security (in logins, permissions based on need, and encryption), reporting, forms inventory, and exports to common statistical packages for analysis. Logging tracks all data entered in REDCap so that it can be traced back to the person who entered it. No data can be changed without showing who has made the changes. This allows the study team to ensure there is security and integrity of the data collected and submitted, there are controls surrounding this aspect. REDCap also provides for principle investigator to sign off on the data, as required in FDA studies. Although users can modify data based on their permissions, they cannot delete the subject or history of that subject. Requests to delete a subject must be made to the REDCap system administrator. Our database system provides for secure web-based data entry with the data stored on servers that we maintain. The data is encrypted during transmission. The servers are located in a secure campus area

with all the appropriate physical security measures in place. The web and database servers are monitored by the TraCS IT staff, patched frequently, and scanned by a third party vendor to ensure that they are protected against known vulnerabilities. The scanning application is the standard service for the entire campus. Access is by individual user id, and is restricted to the forms and/or functions that the user needs to have. The applications themselves are written using open source tools, and have also been scanned by campus security office to ensure that the applications also are protected from known exploits. The data is backed up to electronic media on a daily basis. The electronic media is secured by ITS stored in a secure area separate from the servers.

D. Case ID numbers will indicate the identities of subjects, and this information will be accessible only to the study investigators. All questionnaires will bear case ID numbers only. For all surveys, the research staff will conduct the telephone sessions in a private research office.

E. The web activity data of participants in the SCP+PERC group will be automatically tracked via a built-in feature of the PERC website. The website for PERC is hosted and maintained by the Communication for Health Applications and Interventions (CHAI) Core of the UNC Lineberger Comprehensive Cancer Center. The de-identified web activity data from the PERC website at CHAI will be automatically, electronically transferred (thru SFTP) to the secure IRS database on a weekly basis. CHAI core also provides a secure information technology environment that is a part of the UNC network and complies with UNC security regulations. CHAI core staff engages security protocols similar to the NC TraCS as stated above.

F. A direct link to SignUp Genius will be used within the Forum section of the website to schedule meetings with the health educator during the intervention. The only information that participants will enter to sign up for meetings using SignUp Genius will be their email address, so that SignUp Genius can send them a confirmation of their time slot. The emails they enter can only be seen by the SignUp creator (i.e. health educator), so any emails that participants submit are protected from other group members. Participants will use their ID number to sign up for meetings, so that their identity remains anonymous.

G. The weekly progress information will be aggregated for reports and presented at monthly investigator meetings to determine if any of the study procedures should be altered or stopped. At these meetings, the investigators (including the project coordinator, the interventionist, 2 nurse scientists, 1 physician, 1 public health researcher, and 1 statistician) will review any adverse events, safety concerns or problems (e.g., patients' symptoms of distress), as well as assess study performance related to subject referral, recruitment and retention, protocol adherence, and the quality of the data. The investigators will assess whether the handling of issues related to participants' severe symptom distress has been appropriate and whether there is a need for improvement in the procedures. Our experienced nurse scientist consultant will also be available to discuss and provide consultation on how to ensure data and patient safety.

H. The investigators will perform continuous and close monitoring, with prompt reporting of adverse events to the IRB at UNC-CH and NIH. The investigators and staff will comply with the UNC guidelines for reporting adverse events, which require investigators to report any adverse events that are unexpected, fatal or life-threatening to the IRB using standard forms within 24 hours of the incidents. Additionally, serious adverse events and actions, if any, taken by investigators or the IRB as a result of the event or its continuing review will be reported to the NIH within 24 hours. A complete data and safety monitoring summary report will be submitted to the IRB as part of the annual renewal approval process and to the NIH with the annual progress report.

